## 6.1 Information to be collected on screening failures

All patients/subjects who have signed informed consent but not entered into the next epoch will have the study completion page for the Screening epoch, demographics, inclusion/exclusion, [REDACTED] data collected. [REDACTED]

## 6.2 Patient demographics/other baseline characteristics

Patient demographic and baseline characteristic data to be collected on all patients include: date of birth, age, sex, race, ethnicity and source of patient referral. A detailed medical history (including HF, CV and other conditions relevant to the study population to be enrolled), smoking and alcohol history, and current medical conditions present before the signing of the informed consent will be collected.

MMSE and Echocardiography will be done at screening to determine eligibility for inclusion in to the study.

Investigators will have the discretion to record abnormal test findings on the medical history CRF whenever in their judgment, the test abnormality occurred prior to the informed consent signature.

## 6.3 Treatment exposure and compliance

Compliance will be assessed by the investigator and/or study personnel at each visit using pill counts and information provided by the care giver. This information should be captured in the source document at each visit. The investigator and/or study personnel should counsel the patient if compliance is below 80% at any time during the study. Study drug accountability will be determined by the site monitor while performing routine site visits and at the completion of the study.

The duration of randomized treatment exposure will be calculated based upon the start and stop dates recorded in the dosage administration record (DAR) eCRF.

## 6.4 Efficacy

### 6.4.1 Cognitive function assessment by CCB

The primary endpoint will be change in GCCS from baseline (Visit 201/randomization) to 3 years defined from performance on the seven tasks from the CogState cognitive battery.

1. The Detection test (DET) is a simple reaction time paradigm shown to assess psychomotor function.
2. The Identification test (IDT) is a choice reaction time paradigm shown to assess visual attention.
3. The Continuous Paired Associate Learning (CPAL) visual pattern paradigm shown to assess visual episodic memory.
4. The One Back Test (ONB) is a n-back paradigm shown to assess working memory.

5. International Shopping List Test (ISLT) is a verbal list learning paradigm shown to assess verbal learning.
6. The International Shopping List Test delayed recall (ISLT-DR) is a delayed recall condition from a verbal list learning paradigm shown to assess verbal memory.
7. The Groton Maze Learning Test (GMLT) is a hidden pathway maze learning paradigm shown to assess executive function.

The individual cognitive functions measured by the CogState cognitive battery can be organized into three main cognitive domains;

1. Attention: defined by performance on the Detection, and Identification tests
2. Episodic Memory: defined by performance on the CPAL, ISLT and, ISLT-DR
3. Executive function: defined by performance on the GMLT and ONB test

Performance across these three domains can then be organized to provide a measure of general cognitive function.

These individual cognitive functions and their related cognitive domains have been selected for the current study on the basis that they have been shown to be relevant to characterizing the cognitive impairment that can occur in patients with heart failure and underlying CV disease (Bauer et al 2011). They also have been shown to be associated with both absolute levels of amyloid and rates of changes in amyloid deposition in older adults (Lim et al 2012). The cognitive test battery evaluates the most relevant cognitive domains associated with changes in brain A $\beta$  and changes as a result of progressive CV disease.

The cognitive tests that will be utilized in this study exhibit appropriate sensitivity to detect changes that would occur in the early, prodromal stage of AD, especially in patients positive for amyloid (Lim et al 2014).

Each of the cognitive tests in the CCB will be administered electronically to patients using a computer or tablet in an area suitable for testing without distraction. While subjects themselves perform the tests on the computer or tablet, this performance is guided by an appropriately trained and credentialed rater. The electronic administration ensures standard administration of tests and also means that the CCB can be administered with high fidelity by non-expert but appropriately trained clinical staff (e.g., research assistants or nurses). Assessment with the CCB should take place in a location free from distraction and all site staff nominated to administer the CCB will undergo specific training to ensure that they understand the testing software, the testing processes, the administration of each test and the transfer of test results to CogState. Further details about CogState battery will be provided in CCB manual.

The cognitive test battery will be administered at Screening visit (Visit 1), Visit 103, and randomization visit (Visit 201), and throughout the duration of the study at 6 month intervals, including the end of treatment visit (if prior assessments were performed more than three months ago) and end of study visit (Visit 299).

#### **6.4.2 Individual cognitive domains**

Change from baseline in individual cognitive domains (memory, executive function, and attention) as assessed by composite z-scores by individual components of the cognitive assessment battery at 3 years will be evaluated.

#### **6.4.4 Instrumental activities of daily living as assessed by functional activity questionnaire**

The functional activities questionnaire will be used as a standardized assessment of activities of daily living. This questionnaire is typically used to distinguish normal subjects from subjects with mild to moderate cognitive impairment. FAQ evaluation will be performed at Screening visit (Visit 1), randomization visit (Visit 201), at 6 months (Visit 203), 12 months (Visit 205), 18 months (Visit 207), 24 months (Visit 209), 30 months (Visit 211), end of treatment visit (if prior assessments were performed more than three months ago), and at 36 months end of study (Visit 299). The changes from baseline to 3 years will be analyzed.

#### **6.4.5 Appropriateness of efficacy assessments**

##### **6.4.5.1 Cognitive function assessment**

The comprehensive battery of cognitive tests has been selected as the primary endpoint for this study as it will provide a measure of general cognitive function based on the performance in working memory, executive function, psychomotor speed, visual attention, visual episodic memory, verbal learning and delayed verbal recall.

The CogState Cognitive Battery (CCB) will be used to measure these cognitive domains because the performance measures from tests of these cognitive functions have been validated extensively, including in older patients with heart failure (Clark and McDougall 2006), healthy older individuals with increased levels of amyloid (Lim et al 2014) and in older patients with mild cognitive impairment and clinically classified dementia (Maruff et al 2013). Each test in the CCB has also been designed specifically for the repeated administration necessary in clinical trials in that they are brief to administer, reliable and that once they are learned, repeated administration is not associated with performance improvement, even over relatively short retest intervals (e.g. 1-hour) (Maruff et al 2013, Mielke et al 2014). This validity, brevity and repeatability has meant the performance on the CogState tests is sensitive

to true cognitive change (improvement or decline) in response to disease progression or treatment with pharmaceutical or surgical intervention in various disorders, diseases and injuries.

When considered together the measurement of cognitive function using the CCB enables optimal evaluation of any cognitive decline or cognitive improvement associated with LCZ696 treatment.

#### **6.4.5.2 Individual cognitive domains**

In addition to an overall cognitive function assessment using the GCCS, the three main cognitive domains comprising the GCCS, attention, memory, and executive function, will be further analyzed independently.

These individual cognitive functions and their related cognitive domains have been selected for the current study on the basis that they have been shown to be relevant to characterizing the cognitive impairment that can occur in patients with heart failure and underlying CV disease ([Bauer et al 2011](#)). They also have been shown to be associated with both absolute levels of amyloid and rates of changes in amyloid deposition in older adults ([Lim et al 2012](#)). The cognitive tests that will be utilized in this study exhibit appropriate sensitivity to detect changes that would occur in the early, prodromal stage of AD, especially in patients positive for amyloid ([Lim et al 2014](#)). The cognitive test battery evaluates the most relevant cognitive domains associated with changes in brain A $\beta$  and changes that may occur as a result of progressive CV disease.

#### **6.4.5.4 Instrumental activities of daily living as assessed by functional activity questionnaire**

The functional activities questionnaire (FAQ) will be used as a standardized assessment of instrumental activities of daily living (IADL; [Pfeffer et al 1982](#), [Teng et al 2010](#)). This questionnaire is typically used to distinguish normal subjects from subjects with mild to moderate cognitive impairment. The test is made up of 10 questions that reflect a subject's ability to perform activities of daily living and to function independently. Test scores range for 0 to 30, with a 0 score representing no impairment and a 30 score, as severely impaired. Each of 10 questions is scored from 0, representing normal to 3, dependent on someone else to perform the activity. The FAQ should be administered to the subject and will provide an assessment of patient's physical and social functioning.

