#### Study Population:

The study population will consist of patients 60 years and older with chronic heart failure (NYHA class II-IV) and LVEF > 40%. LCZ696 has been shown to improve survival and reduce heart failure-related hospitalization in patients with HFrEF (LVEF ≤ 40%). Hence the study population consists of patients with HFpEF (LVEF >40%), as it is considered unethical to randomize HFrEF patients in this long term study to the valsartan treatment group. HFpEF is a condition that predominantly affects an elderly population. Age is also an important risk factor for cognitive decline and amyloid deposition. The entry requirement of 60 years or older and symptomatic heart failure will ensure that patients who are likely to benefit from LCZ696 therapy are included in the study while allowing the ability to study the potential effects on cognitive function in a relevant population. As treatment with LCZ696 has been demonstrated to confer significant mortality and morbidity benefit compared to current standard of care (ACEI) to patients with HFrEF, these patients will be excluded from the study. However, given the similarity of the population and patient characteristics, the results of this study should be relevant to the heart failure population at large regardless of ejection fraction.

The study aims to assess the effect of LCZ696 compared to valsartan on cognitive function in patients with normal cognition and mild cognitive impairment (MCI), while excluding patients with significant impairment, (e.g. patients with an MMSE score of <24; [Holsinger et al 2007](#)). Available data suggest that amyloid plaque deposition may reach a plateau once a patient is clinically diagnosed with AD ([Bateman et al 2012](#)). The rate of cognitive decline in AD patients is not uniform as it is dependent on various factors. Hence patients with a clinical diagnosis of AD or dementia will also be excluded from this study.

Further details about the patient population are provided in [Section 4](#).

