In addition, NYHA class assessment, concomitant medications, review of inclusion/exclusion criteria, drug accountability, AE/SAE, should also be done at Visit 199. To allow patients to be randomized at Visit 201, patients should have a PET scan scheduled at Visit 199 (for all patients participating in the substudy) since it may take up to 5 days following the scan for the brain images to be centrally read. PET scan should be scheduled only after confirming that the patient fulfills all inclusion and exclusion criteria, safety criteria and is eligible for randomization.

Following completion of the PET scan, all patients will be randomized at Visit 201. The CogState Cognitive Battery, FAQ, APOE4, and plasma beta-amyloid assessments will all be performed at Visit 201.

End of run-in assessments (Visit 199) and assessments for randomization (Visit 201) are reflected at Visit 199/201 in [Table 6-1](#).

Visit 201 will be considered the reference visit for all study visits during the randomized treatment epoch. Regardless of the occurrence of any unscheduled visits, scheduled visits should be performed within the specified timeframe in relation to Visit 201 as outlined in [Table 6-1](#). If a visit is completed earlier than scheduled or postponed, it should not result in the next visit being brought forward or postponed.

[figure not shown]
Patients will have regular clinic visits performed for the first 6 months (up to and including Week 26). Thereafter, patients will have clinic visits alternating with telephone contact visits every 3 months.

Patients/subjects will be contacted for safety evaluations during the 30 days following the last administration of study treatment.

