Note that negative sign is included in the calculation for tasks where increasing values indicate worsening performance (i.e.,  $Z_{DET}$ ,  $Z_{IDT}$ ,  $Z_{ONB}$  and  $Z_{GMLT}$ ) so that for all standardized change scores negative values indicate a decline from baseline while positive scores indicate improvement from baseline.

These seven individual z-scores are then combined to generate the GCCS:

CogState GCCS = average of ( $Z_{DET}$ ,  $Z_{IDT}$ ,  $Z_{CPAL}$ ,  $Z_{ONB}$ ,  $Z_{ISLT}$ ,  $Z_{ISLT-DR}$ ,  $Z_{GMLT}$ )

The composite score will be computed if five of the seven tests are completed and the five tests provide an assessment of the three cognitive domains as defined below being assessed. That is, a composite score requires that each cognitive domain be measured by at least one cognitive test.

In addition to the GCCS, composite scores for three main subdomains memory, attention and psychomotor function will also be generated by combining the standardized change from baseline scores for individual tests from the CCB using the following formulae:

- Composite score of memory tests = average of ( $Z_{CPAL}$ ,  $Z_{ISLT}$ ,  $Z_{ISLT-DR}$ )
- Composite score of executive function tests = average of ( $Z_{ONB}$ ,  $Z_{GMLT}$ )
- Composite score of attention tests = average of ( $Z_{DECT}$ ,  $Z_{IDT}$ )

Each composite score will be the average of the non-missing individual test z-scores

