#### 9.4.2 Statistical model, hypothesis, and method of analysis

The change from baseline in the GCCS of CogState test battery will be analyzed using a repeated measures analysis of covariance (ANCOVA) model in which treatment, age stratification factor, MMSE stratification factor, education level, APOE4 status (carrier vs. non-carrier), baseline cerebrovascular disease burden as measured by MRI (calculated based on four factors: lacunar infarcts > 2; cortical or subcortical infarct > 1cm^3; white matter lesion

Fazekas score of 3; micro hemorrhages  $\geq 4$ ), visit (Weeks 26, 52, 78, 104, 130 and Week 156) and treatment-by-visit interaction are included as fixed-effect factors and baseline GCCS and visit by baseline GCCS interaction as covariates, with a common unstructured covariance matrix among visits between treatment group. The adjusted mean changes at 3 years (Week 156) within each treatment, the difference in mean changes at 3 years (Week 156) between the two treatments, and its 95% confidence interval obtained from the above model will be presented. In addition, the treatment difference (LCZ696-valsartan) in mean changes from baseline to 3 years will also be expressed based on a standardized effect size (Cohen's d) with a 2-sided 95% confidence interval. The Cohen's d will be estimated by using the adjusted between-treatment mean difference, divided by the estimated standard deviation, which is calculated from the standard error of the adjusted mean change and the sample number of patients within each group (the pooled SD) from the above modeling. The analysis is based on likelihood method with an assumption of missing at random (MAR) for missing data.

As the primary analysis, this repeated measure ANCOVA model will be performed in the Safety set including 'on-treatment' data collected prior to the start of treatments for AD or cognitive impairment. The Cohen's d based on the adjusted difference in mean changes at 3 years (Week 156) between two treatments and its 95% confidence interval from this model will be used to draw the main conclusion for the primary objective. On-treatment data refer to cognitive test data collected while patients are on-study-medication (regardless of treatment interruption) or within three months after final study drug intake date.

In addition, the same repeated measure ANCOVA model will be performed in the following two analysis sets as supportive analyses:

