2.5.2 Statistical hypothesis, model, and method of analysis

The change from baseline in the GCCS of CogState test battery will be analyzed using a repeated measures analysis of covariance (ANCOVA) model in which treatment, age stratification factor, MMSE stratification factor, education level, APOE4 status (carrier vs. non-carrier), baseline cerebrovascular disease burden, visit (Weeks 26, 52, 78, 104, 130 and Week 156) and treatment-by-visit interaction are included as fixed-effect factors and baseline GCCS and visit-by-baseline GCCS interaction as covariates, with a common unstructured covariance matrix among visits between treatment groups. The adjusted mean changes at 3 years (Week 156) within each treatment, the difference in mean changes at 3 years (Week 156) between the two treatments, and its 95% confidence interval obtained from the above model will be presented. In addition, the treatment difference (LCZ696-valsartan) in mean changes from baseline to 3 years will also be expressed based on a standardized effect size (Cohen's d) with a 2-sided 95% confidence interval. The Cohen's d will be estimated by using the adjusted between-treatment mean difference, divided by the estimated pooled standard deviation. The estimated standard deviation for the mean difference is:

$$SD = \left(\frac{1}{n_1} + \frac{1}{n_2} \right)^{1/2} \hat{\sigma}$$

where n1 and n2 are the number of patients within each treatment group and $\hat{\sigma}$ is the pooled standard deviation of the within treatment group adjusted mean change. Cohen's d can be rewritten in terms of t value of the estimated between treatment group difference based on the adjusted mean changes from the model mentioned above:

$$t = \frac{\hat{\mu}_1 - \hat{\mu}_2}{SD} = \frac{\hat{\mu}_1 - \hat{\mu}_2}{\left(\frac{1}{n_1} + \frac{1}{n_2} \right)^{1/2} \hat{\sigma}}$$

$$\hat{d} = \frac{\hat{\mu}_1 - \hat{\mu}_2}{\hat{\sigma}} = \left(\frac{1}{n_1} + \frac{1}{n_2} \right)^{1/2} \times t$$

Confidence interval (CI) of Cohen's d is based on 95% CI of the noncentrality parameter of t value divided by the square root of the degrees of freedom from the estimated between treatment group adjusted mean change (Cumming and Finch 2001). The analysis is based on a direct likelihood method with an assumption of missing at random (MAR) for the missing data mechanism.

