2.6.2 Statistical hypothesis, model, and method of analysis

For secondary efficacy variables composite z-scores by individual domain (memory, executive function and attention) and IADL, the changes from baseline to 3 years will be analyzed using the same repeated measures ANCOVA model as described in [Section 2.5.2](#) but with baseline GCCS replaced with respective secondary variable baselines. The adjusted mean changes at 3 years (Week 156) within each treatment, the difference in mean changes at 3 years (Week 156) between two treatments, its 95% confidence interval obtained from the above model will be presented. In addition, the treatment difference (LCZ696-valsartan) in mean changes from baseline to 3 years will also be expressed in terms of a standardized effect size (Cohen's d) with a 2-sided 95% confidence interval. The Cohen's d will be estimated as in a similar manner as planned for the primary endpoint analysis ([Section 2.5.2](#)). The analysis is based on likelihood method with an assumption of missing at random for missing data, and will be performed in the Safety set including 'on-treatment' data collected prior to the start of treatments for AD or cognitive impairment. On-treatment data are those collected while patients are on-study-

medication (regardless of treatment interruption) or within three months after final study drug intake date. This analysis will be performed in the SAF.

In addition, as supportive analysis, similar repeated measure ANCOVA model will also be performed for these secondary endpoints for all data in the FAS.

Summaries of absolute values and change from baseline by treatment group and visit will be presented. Figures will be produced to visually show the endpoint values (composite z scores by cognitive domain and IADL) by visit over the study period for each treatment group.

These analyses will be done in both SAF and FAS, for 'on-treatment' data and for all data, respectively.

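### The FAQ model swaps baseline GCCS for baseline FAQ instead of keeping both, so a two-level MMSE factor is its only direct measure of baseline cognition

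*Protocol*

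**What the plan says.** The primary model (Protocol 9.4.2, SAP 2.5.2) has "baseline GCCS and visit by baseline GCCS interaction as covariates". Its other baseline and design terms are "treatment, age stratification factor, MMSE stratification factor, education level, APOE4 status (carrier vs. non-carrier), baseline cerebrovascular disease burden", together with visit and treatment-by-visit.

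For memory, executive function, attention and IADL/FAQ, Protocol 9.5.1 and SAP 2.6.2 agree: the same model is used, "but with baseline GCCS replaced with respective secondary variable baselines". Neither document gives a reason for substituting rather than adding.

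Both measures come from one visit (Protocol 6): "The CogState Cognitive Battery, FAQ, APOE4, and plasma beta-amyloid assessments will all be performed at Visit 201". On the FAQ scale (Protocol 6.4.5.4): "Test scores range for 0 to 30, with a 0 score representing no impairment".

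The main FAQ analysis uses on-treatment data in the Safety set up to the start of any drug for Alzheimer's disease or cognitive impairment. A supportive model uses all data in the FAS. Both assume missing at random (MAR). SAP 2.6.3 on missing secondary data restates MAR, and SAP 2.6.4 gives only a mis-stratification analysis.

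**The concern.** After the substitution, the FAQ model still holds age stratum, education, APOE4 status and cerebrovascular burden. Cognition itself enters only through a two-level MMSE factor, in patients already selected at MMSE 24 or above. A continuous seven-test score from the same visit is left out.

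Two features of the plan make that score relevant to FAQ:

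- **Link to cognition.** Protocol 3.2 chose FAQ because cognitively demanding daily activities fail early in the path to dementia, and presents it as a complement to GCCS. On that reasoning, baseline GCCS plausibly predicts FAQ decline.
- **Missing data.** Starting a cognition drug probably depends on cognition, and it ends a patient's FAQ data in the main analysis. Protocol 9.4.3 explains that missing values are represented by patients with similar covariates and histories, so the covariate list affects how credible MAR is. For GCCS, SAP 2.5.5 concedes that patients who start these drugs might have declined faster than MAR predicts, and it adds tipping-point and joint-model analyses. FAQ has no such analysis.

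At stake is some precision on one secondary endpoint and the credibility of its MAR assumption.

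**Working it through.** **1. The plan's own figure.** The only sizing for a cognitive endpoint is for GCCS: d = 0.3, two-sided 95% interval, at least 80% probability, 180 per group, 30% drop-out, 520 randomised (Protocol 9.8.1 and 9.8.3).

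- n per group = 2 × (1.960 + 0.842)² / 0.3² = 174.4, so 175 against 180 stated.
- Power at 180: 0.3 / √(2/180) = 2.846; Φ(2.846 − 1.960) = 0.812.
- 360 / 0.70 = 514.3, so 515 against 520 stated.

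The figures reproduce. They do not change under the proposal, because the primary model already contains baseline GCCS. The documents give no SD, margin or power for FAQ.

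**2. Gain from retaining baseline GCCS.** Let r be the partial correlation of baseline GCCS with 3-year FAQ change, given baseline FAQ and the covariates kept. Residual variance is multiplied by 1 − r² and interval width by √(1 − r²). The equivalent sample size is 360 / (1 − r²). Power below is illustrative only, for a standardised difference of 0.3 at 180 per group.

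| r (assumed) | Variance reduction | Interval width reduction | Equivalent N | Illustrative power |
|---|---|---|---|---|
| 0 | 0% | 0% | 360 | 0.812 |
| 0.1 | 1% | 0.5% | 364 | 0.816 |
| 0.2 | 4% | 2.0% | 375 | 0.828 |
| 0.3 | 9% | 4.6% | 396 | 0.847 |

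**3. Does the floor at 0 drive the gain?** A simulated 0–30 score was floored so that 57% to 93% of baselines were 0 (assumed shares). Latent function correlated 0.2 to 0.6 with GCCS, and GCCS had a varying extra link to later decline. The models compared were baseline FAQ alone and baseline FAQ plus GCCS.

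- No extra link to decline: variance reduction of at most 1.9% at any floor.
- Strongest link assumed: 19.6–21.8% with 57% at 0, but 9.4–10.8% with 93% at 0.

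The gain comes mainly from GCCS predicting decline. A heavier floor did not enlarge it when that link was strong. This simulation left out the other covariates, so its sizes are not estimates for this trial.

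**4. The domain scores.** On GCCS: "These seven individual z-scores are then combined to generate the GCCS"; the same z-scores form the domains. With equal inter-test correlation c, the correlation of a k-test domain baseline with GCCS is √{[(1 + 6c)/7] / [(1 + (k − 1)c)/k]}.

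- c = 0.2, k = 2: √(0.314 / 0.600) = 0.72.
- c = 0.5, k = 3: √(0.571 / 0.667) = 0.93.

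Over an assumed c of 0.2 to 0.5, the domain baseline already carries much of what GCCS would add.

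**The case against.** **The analysis is standard.** Protocol and SAP agree, adjusting for the endpoint's own baseline is accepted practice, and randomisation protects the comparison with or without GCCS. This stands: it is an optional improvement, not an error.

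**The model is not bare.** APOE4 status, education and cerebrovascular burden stay in, and the likelihood uses each patient's earlier FAQ values. This stands and limits the gain. None of these terms, however, measures baseline cognition directly.

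**All-data FAS model.** It keeps FAQ values after a cognition drug starts, which answers part of the censoring worry. It still assumes MAR with the same covariates, so it does not test that assumption.

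**Adding GCCS could lose patients.** GCCS needs at least five of seven tests covering all three domains. At r = 0.1 the gain equals about 4 patients in 360, so losing four would cancel it. The risk is small: the battery is also given at screening and Visit 103, and SAP 2.1.1 fills a missing randomisation value with the most recent earlier one.

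**Stronger readings that a reader might infer.** One is that the swap matters because FAQ sits at its floor. The study enrols patients "in patients with normal cognition and mild cognitive impairment (MCI), while excluding patients with significant impairment", so a floor is plausible. But the documents give no FAQ distribution, FAQ also reflects physical and social functioning in symptomatic heart failure, and step 3 does not show the floor as the source of the gain. Another is that the domain models need the same change, because "the three main cognitive domains comprising the GCCS, attention, memory, and executive function, will be further analyzed independently". Step 4 shows why little would be expected there.

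**Conclusion.** The point holds for FAQ only, as a small and unquantified improvement to a valid analysis. The FAQ model leaves out a baseline cognition score that is already collected, and FAQ has no not-at-random analysis to test its MAR assumption.

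The size depends on r, which the documents do not give. Over an assumed r of 0 to 0.3, residual variance falls by 0% to 9% and the interval narrows by 0% to 4.6%. The MAR benefit cannot be put into figures. It rests on the assumption that starting a cognition drug depends on baseline cognition beyond what the model already holds.

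The documents do not support reading this as bias, as a consequence of the FAQ floor, or as a reason to change the domain models. No stated figure is wrong, and the planned 520 is unaffected. Priority: nice to have.

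**What to change.** In SAP 2.6.2, and Protocol 9.5.1 if it is amended, treat IADL/FAQ separately: use the Section 2.5.2 model with baseline FAQ and visit-by-baseline FAQ added, and with baseline GCCS and visit-by-baseline GCCS retained. Missing baselines follow SAP 2.1.1. If the model does not converge, remove visit-by-baseline GCCS first, before the steps already listed in SAP 2.5.2. Leave the domain models as they are.

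At minimum, pre-specify this as a supportive FAQ model. Either way, settle it before unblinding, since a covariate added later is open to challenge.

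The cost is one line of SAP text and six fixed-effect parameters (one baseline GCCS slope for each of six visits). No new data or patients are needed.
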